 - The subject must have been diagnosed with episodic migraine headache at least six months prior to entering into the Study, consistent with the International Headache Classification of Headache Disorders (ICHD-II and ICHD-III beta) guidelines.
 - The subject must have a history of at least three consecutive months of stable migraine headaches prior to entering the study. The subjects will not have had changes in medication usage (prescription medications for migraine headache) for the three months leading up to the study, nor will they introduce new medications during the study period. (The primary focus is on prescription medications for migraine headache. However, medications that are prescribed for co-morbid conditions which also have

demonstrated efficacy for migraine prevention should not be altered in this time period.)

- Subjects will satisfy these criteria: On a monthly basis, at least four, and not more than a total of fourteen (4-14), headache days of which between four and fourteen (4-14) are migraine headache days, as judged by the subject.
- The subject must not have failed on more than two classes of properly administered prophylactic pharmaceutical therapies for migraine headache. The subject may be on a single migraine prophylactic drug as long as the dosage has not been altered within three months of starting the study and the dosage must not be altered for the duration of the study;
- The Investigator must have confidence in the subject's ability to reliably use the CVS device and promptly complete the electronic daily headache diary forms. The daily headache diary will be completed from the beginning of the pre-treatment baseline period through the end of the study. The diary is described more fully below and in the definitions section at the end of this document.

• **Exclusion Criteria:** Individuals who:

- have previously participated in a clinical trial using the CVS Device
- are pregnant
- using more than one concurrent prophylactic pharmaceutical therapy for migraine headache
- have a history of cardiovascular disease
- work night shifts
- have been diagnosed with vestibular migraine
- have menstrual migraine exclusively
- have been diagnosed with post-traumatic migraine
- have a history of unstable mood disorder or unstable anxiety disorder. Specifically, a BDI-II score of 20 or greater and/or a BAI score of 16 or greater will disqualify a patient from randomizing into the treatment portion of the study.
- use a hearing aid

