- have a cochlear implant
- have chronic tinnitus
- have temporomandibular joint disease
- have been diagnosed with traumatic brain injury
- have been diagnosed with neurological disease other than headaches

- have a diagnosed vestibular dysfunction and/or balance dysfunction
- have a history of abusing alcohol or other drugs
- are experiencing medication overuse headaches (individuals with respect to whom the principal investigator is concerned that analgesic abuse is involved based on the ICHD-II guidelines).
- are less than 18 years old or greater than 65 years old
- have had eye surgery within the previous three months or ear surgery within the previous six months
- have active ear infections or a perforated tympanic membrane
- have participated in another clinical trial within the last 30 days or are currently enrolled in another clinical trial
- are using Botulinum toxin-based treatments for migraines or for facial cosmetic reasons.
- are taking anti-emetics chronically (more than 2 times per week, consistently)
- Though not excluded, subjects taking anti-histamines will be encouraged not to take such medications within four hours prior to a CVS treatment. The investigator should review other medications taken by the subject with properties that mimic anti-nausea or anti-dizziness drugs as these may reduce responsiveness of the vestibular system to caloric stimulation. Such medications should also be avoided within four hours prior to a CVS treatment.

- **Withdrawal Criteria**

- Subjects must be withdrawn from the clinical trial if any of the following events occur:
 - Surgery during the study period.
 - A subject does not continue to meet inclusion/exclusion criteria.
 - A subject is significantly non-compliant with the requirements of the protocol (principal investigator & sponsor decision).
 - The subject does not complete at least 25 of 28 daily diary entries in her/his headache diary during the baseline period. (That is, the subject must be compliant with maintaining the headache diary.)
 - A subject becomes pregnant during the trial as evidenced by a positive pregnancy test.
 - The subject develops an illness (adverse event) that would interfere with his/her continued participation.
 - The subject withdraws his/her consent.
 - The principal investigator feels that it is the subject's best interest to be withdrawn.
 - Scion Neurostim discontinues the study or has achieved the targeted enrollment.

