If the subject is discontinued from the participation in the study for any reason, the principal investigator must make every effort to perform all evaluations for the final visit and document the reasons for discontinuation. If a subject withdraws due to an adverse event, the study coordinator will follow up with regular phone calls to document the resolution of the event.

Though a subject will not be withdrawn from the study if she/he exceeds 14 headache days in any of the treatment months, such subjects will be grouped separately during the final study analysis. The rationale for this grouping is that a large percentage of subjects in the first CVS migraine RCT were excluded from randomization because they exceeded 14 headache days, thus calling into question their stable episodic status. If a subject has a “good month” during baseline, but is potentially unstable, she/he might be recruited into the study in violation of the aim of enrolling stable EM subjects. No evidence that the CVS device increased headache burden was seen in the first RCT. However, we will continue to follow subjects who exceed 14 headache days in a month during the treatment period so as to gather more data on this sub-population.

- **Concomitant Medications**

- The use of acute abortive medications for the symptomatic treatment of migraine headache will be allowed during the clinical trial. Subjects may use their usual acute abortive medications, and medications should not be changed during the clinical trial. A treated migraine headache is one for which a subject has taken an acute abortive medication (prescription medication, not OTC).
- The subject may be on a single migraine prophylactic drug as long as the dosage has not been altered within three months of starting the study and the dosage must not be altered for the duration of the study. The subject must not have failed on more than two classes of properly administered prophylactic pharmaceutical therapies for migraine headache. Prophylactic medications used to treat other medical conditions may be used, at the principal investigator's discretion, if the subject is taking a stable dose for at least three months prior to screening and continues throughout the study.

3) Pivotal Study Size; Randomization

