The design size contemplates enrolling up to one hundred and twenty (120) subjects who will successfully follow through to completion of their participation in at least the first treatment portion of the study (first 3-month treatment period). The subjects will be randomly assigned to: twice-per-day active, once-per-day active or twice-per-day placebo in a 1:1:1 ratio.

The results of the first migraine RCT did not show evidence of stratification based on gender or clinical site or baseline headache frequency. Envelopes containing

randomization assignments will be grouped in batches of six, each batch containing two of each of the three assignment arms. The batches of envelopes will be randomly shuffled by an agent not involved with the study. A given batch will be completed before the next batch is opened. This procedure results in 20 possible different arrangements, for six subjects, of the ordering of treatment and placebo assignments. The unblinded coordinator will record the subject's designation but will not share the assignment with the subject, principal investigator, or statistician. Each study site will be individually randomized (no central randomization).

The assessment of the primary endpoint will be completed by a blinded, central statistician. The subjects will be told, within the informed consent document, of the existence of a placebo arm. Subjects will be told that the device stimulates the brain stem. Subjects will be told that they will receive at least 3-months of active treatment during the 6-month treatment period. In fact, subjects in the placebo arm in the first 3-month period will be switched to active in the second 3-month period. Subjects will be asked to guess (and provide reasons) about their treatment assignment at the end of the first 3-month treatment period and at the end of the second 3-month treatment period. Subjects will also be asked, after their very first treatment in the clinic, a series of questions designed to assess the quality of blinding (to provide evidence that the placebo device is an effective sham).

4) Study Schedule; Subject Enrollment and Activities

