- (i) **Screening & Baseline Period:** Once the subject has been established as having the appropriate pre-treatment history, she/he will be asked to complete a review of the informed consent. If the subject agrees to participate in the study, the subject will then complete a screening visit. The study coordinator will complete a headache history questionnaire for the subject. If the subject is recommended for continuation in the study after the screening visit and tentatively approved by a principal investigator, she/he will start a daily headache diary and continue to make entries for twenty-eight consecutive days. Subjects will be given Scion email accounts to be used for submitting headache diary entries. Sites will assist subjects with syncing their Scion email accounts with their smartphones or tablets, and will ensure that subjects can competently take a photo of the ediary form, upload and send according to procedure. If the subject does not complete at least 25 of 28 daily headache diary entries during the baseline period, she or he will be withdrawn and will not proceed to randomization.
- (ii) **Clinic Training Visit:** After enrollment, the completion of one month of daily headache diary entries, and reconfirmation by the relevant investigator of the subject's participation in the study, the subject will come to the clinic for an appointment(s) for training on the use of the CVS device. During the clinic visit, the subject will complete a quality of life (QOL) assessment. The assessment will consist of the HIT-6, BAI, BDI-II and Pittsburgh Sleep Quality Assessment questionnaires. The BAI and BDI-II scores will be tallied with the following outcomes:
 - a. Subjects who score 20 or higher on the BDI-II or answer affirmative to questions 9 on the BDI-form will not proceed to randomization and will be withdrawn from the study.
 - b. Subjects who score 16 or higher on the Beck Anxiety Index will not proceed to randomization and will be withdrawn from the study.

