- (iii) Also, women of childbearing age will complete a urine-based pregnancy test to reconfirm that they are not pregnant. The unblinded coordinator will open, at random, an envelope assigning the subject to one of the three study arms. The clinic period is described below. During the first visit, the subject will complete a training session based on a set training module. The subject will complete a proficiency evaluation and the study coordinator will certify the subject's proficiency in the use of the CVS device. The study coordinator will

complete a visit assessment form. At the end of training, a first usability questionnaire will be completed by the subject.

(iv) **First Treatment Period:** The eighty-four days (3 months) following the pre-treatment baseline period constitute the first treatment period. This is the test period, the results from which will be measured against the pre-treatment baseline period data in assessing the study endpoints. Specifically, data from the last month of the first treatment period will be compared with the one-month-long pre-treatment baseline period. As close as possible (as scheduling permits) to two weeks after the start of treatment, a clinical visit will occur and another visit assessment form will be completed. A second usability questionnaire will be completed. The subject will be asked to bring the CVS device to the clinic to perform a treatment in front of the unblinded study coordinator to reaffirm proficiency in using the device. Any issues related to balance or other safety concerns will promptly be referred to the site principal investigator, who can terminate the subject's further participation in the study if necessary.

(v) **End of First Treatment Period – Start of Second Treatment Period:** At the end of the first treatment period the subject will be asked to return to the clinic and will be asked to complete the QOL questionnaires and a third usability questionnaire. All subjects will receive new SD cards for the second treatment period and the old SD cards will be retained so that treatment compliance logs can be extracted. All subjects will receive active treatment cards with the following assignments (first treatment period -> second treatment period):

- BID placebo -> BID active
- BID active -> BID active
- QD active -> QD active

Subjects will perform a treatment in front of the unblinded coordinator to re- confirm their ability to properly use the device.

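### The primary analysis is declared intent-to-treat but admits only subjects with at least 25 month-3 diary entries, so most subjects withdrawn in period 1 are left out with no stated handling

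*Combined protocol and SAP*

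**What the plan says.** **Analysis rule.** Section 8 (Statistical Analysis and Study Size) names intent-to-treat as the approach for the primary aim. The same paragraph restricts analysis of the primary endpoint to subjects with 25 or more diary entries in the relevant 28-day month. The endpoint is baseline month minus treatment month 3, so the relevant month is month 3. Neither Section 8 nor any other section gives an imputation rule or model for subjects who fall short.

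**Withdrawal.** Section 2 (Withdrawal Criteria) opens with "Subjects must be withdrawn from the clinical trial if any of the following events occur". The list includes surgery, illness, significant non-compliance, no longer meeting eligibility, and investigator judgement. Section 4(iv) likewise refers safety concerns to the site investigator, "who can terminate the subject's further participation in the study if necessary". These texts end study participation, not only device use.

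**After withdrawal.** For discontinuation for any reason, Section 2 says "the principal investigator must make every effort to perform all evaluations for the final visit and document the reasons for discontinuation". After an adverse event withdrawal, "the study coordinator will follow up with regular phone calls to document the resolution of the event". Nothing there asks for the diary to continue.

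**One group is kept.** Section 2 also says "a subject will not be withdrawn from the study if she/he exceeds 14 headache days in any of the treatment months".

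**Target.** Section 3 sizes the trial as up to 120 "subjects who will successfully follow through to completion of their participation in at least the first treatment portion of the study". Section 7 starts the primary analysis when 120 have completed period 1.

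**The concern.** Intent-to-treat means that subjects are compared as randomised, whatever happens to them later. Here, inclusion depends on a post-randomisation event: still being in the study, and still keeping the diary, through month 3. The label and the analysis set disagree.

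This matters if leaving is related to outcome or differs by arm. The plan gives reasons to allow for both. The Subject Disposition Form lists adverse event and lack of efficacy among the reasons for discontinuation. Section 6 names dizziness and vertigo among the more likely device effects, while Section 5 says that placebo subjects receive no material caloric stimulation. The inclusion criteria say of subjects, "nor will they introduce new medications during the study period". Read with the rule that subjects must continue to meet eligibility, this could remove someone who starts a new preventive because migraine is not controlled.

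Section 4 treats baseline plus period 1 as a complete trial in its own right, so this comparison carries the main conclusion.

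**Working it through.** **Step 1: who is excluded.** Period 1 has 84 days. Month 3 is days 57 to 84. The earliest day on which a subject can have 25 month-3 entries is 56 + 25 = day 81. A subject withdrawn before about day 81 is therefore outside the primary analysis. A subject withdrawn after that with a full diary is inside, as is a subject who under-uses the device but stays and keeps the diary. A subject who stays but has fewer than 25 entries is also outside.

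**Step 2: reproduce the plan's figure.** Inputs from Section 8: 40 per arm, SD 3.36, difference 2.13 days, alpha 0.05. A two-sided two-sample t-test gives power of 80.0%, as stated. The standard error of the difference is 3.36 × √(2/40) = 0.75 days.

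**Step 3: share left out.** Section 8 expects 5 dropouts per group in each 3-month period. Section 3 counts completers, so 40 completers plus 5 leavers makes 45 randomised per arm, and 5/45 = 11.1%. If 40 were instead the number randomised, the share would be 5/40 = 12.5%. Applying the figure to period 1 is an assumption.

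**Step 4: possible bias.** The first trial's month-3 reductions (Background) were 3.6 days active and 0.9 placebo, a difference of 2.7. Take this as the completer difference. Let each gap be the number of days by which leavers do worse than completers in the same arm. Then

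overstatement = share × (active gap − placebo gap).

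| Assumed leaver outcomes | Calculation | Overstatement (days) |
|---|---|---|
| Active leavers 1 day worse, placebo the same | 0.111 × 1 | +0.11 |
| No reduction in leavers of either arm | 0.111 × (3.6 − 0.9) | +0.30 |
| Active leavers have no reduction, placebo the same | 0.111 × 3.6 | +0.40 |
| Equal gaps in both arms | 0.111 × 0 | 0 |
| Placebo leavers 1 day worse, active the same | 0.111 × (−1) | −0.11 |

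Relative to the standard error, +0.11 to +0.40 is 0.15 to 0.53.

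**Step 5: power if leavers are followed.** Take SD 3.36 within completers and within leavers, placebo leavers the same as placebo completers, and active-arm variance 3.36² + 0.111 × 0.889 × gap².

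| Case | Difference | Active SD | Power |
|---|---|---|---|
| 40 completers per arm | 2.70 | 3.36 | 94.4% |
| 45 followed, active gap 1 | 2.59 | 3.375 | 95.0% |
| 45 followed, active gap 2.7 | 2.40 | 3.465 | 91.0% |
| 45 followed, active gap 3.6 | 2.30 | 3.545 | 87.8% |

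**Step 6: partial recovery.** If 3 of 5 leavers per arm are followed (an assumption), 43 per arm are analysed. With an active gap of 1 the estimate is 2.70 − (3/43) × 1 = 2.63, leaving 2.63 − 2.59 = 0.04 days of bias. With a gap of 3.6 it is 2.70 − (3/43) × 3.6 = 2.45, leaving 0.15 days.

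**The case against.** The strongest reply is that the early-termination sentence is ordinary and excludes nobody; the 25-entry rule in Section 8 does that, and it also drops subjects who never withdraw. This stands, so the first change belongs in Section 8. The withdrawal text still adds to the problem, because it leaves no month-3 diary for any analysis to use.

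A second reply is that the inclusion criteria describe the diary as running from baseline to the end of the study. That is general wording within an eligibility criterion and does not say that withdrawn subjects continue. Equally, nothing forbids them to.

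A reader might infer that the Early Termination form, with no diary item, and the blank diary cell in that schedule column show a decision to stop the diary. They do not. The column is shared with the week-40 final visit, and the completers' final form has no diary item either. The point rests on the silence of the withdrawal text.

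A reader might also infer that the omission favours the device. The documents do not show this. Subjects are told that they will receive at least three months of active treatment and that the time to benefit is unknown, which gives non-responders a reason to stay through period 1. Subjects above 14 headache days are kept. The visit forms merely record medication changes. Lack of efficacy is one box on a form used for the whole study.

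Finally, 5 per group is an expectation, not a maximum, and comes from a sentence on power for later endpoints. It may describe only attrition after period 1 (40 to 35 to 30), in which case the plan gives no period-1 figure. Neither 11% nor 15 subjects is a ceiling.

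**Conclusion.** The point holds. Followed as written, the plan produces an analysis of subjects who stayed and kept diaries, under an intent-to-treat label. This is a conflict between a stated rule and a declared principle, not only a missing detail.

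The likely size is modest. About 11% per arm would be missing if the expected dropout applied to period 1. The bias range of −0.11 to +0.40 days includes zero and is at most about half a standard error. At the upper end, 2.3 days of a 2.7-day effect would remain, still above the 2.13-day detectable difference. Every leaver outcome in that range is assumed. The sample size calculation is correct, and if 40 means completers the issue is what is being estimated, not lost power.

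The change should be made, but the documents do not support a claim that the trial would fail or that its result would be biased in a known direction.

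**What to change.** 1. **Section 8.** Define the intent-to-treat primary analysis as all randomised subjects with any post-baseline diary data, for example a repeated-measures model over months 1 to 3 with the month-3 contrast as primary. Keep the 25-entry analysis as a sensitivity analysis. Fix this before unblinding.
2. **Section 2, Withdrawal Criteria.** Keep the reasons for stopping, but separate stopping the device from leaving the study. Unless consent is withdrawn, ask subjects who stop in period 1 to continue the diary and the two-weekly calls to day 84. State that counting days after a new preventive is a treatment-policy choice, and add a sensitivity analysis without those days.

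Continued diaries alone would not be enough, because the 25-entry rule would still drop sparse diaries.

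**Cost.** A short amendment and a consent line, plus up to 12 weeks of diaries and calls for roughly 15 subjects (3 × 5) if 5 per group leave. No new tool is needed: Section 4(i) already provides that "Subjects will be given Scion email accounts to be used for submitting headache diary entries", off-device diary keeping is already planned for the observation period, and the calls exist. Off-device months may dilute the effect: power is about 88 to 95% with all 45 per arm followed, against 94% with 40 completers. Consent withdrawals and losses to follow-up stay missing at month 3, and a subject with no post-baseline diary at all still contributes nothing. Diaries that were never requested cannot be recovered later, so the change has to come while subjects are in period 1.

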• have been diagnosed with neurological disease other than headaches		
• have a diagnosed vestibular dysfunction		
• abuse alcohol or other drugs		
• are experiencing medication overuse headaches (individuals with respect to whom the principal investigator is concerned that analgesic abuse is involved based on the ICHD-II guidelines).		
• are less than 18 years old or greater than 65 years old		
• have had eye surgery within the previous three months or ear surgery within the previous six months		
• have active ear infections or a perforated tympanic membrane		
• have participated in another clinical trial within the last 30 days or are currently enrolled in another clinical trial		
• are using Botulinum toxin-based treatments for migraines		
• are taking anti-emetics chronically		

Please Note: Though not excluded, patients taking anti-histamines will be encouraged not to take such medications within four (4) hours prior to a CVS treatment. The investigator should review other medications taken by the patient with properties that mimic anti-nausea or anti-dizziness drugs as these may reduce responsiveness of the vestibular system to caloric stimulation. Such medications should also be avoided within four (4) hours prior to a CVS treatment.

Demographics:**Complete or Circle**

Date of Birth: (dd/mmm/yyyy)	/	/
Gender:	Male	Female

SUBJECT ID: _____
DATE: _____SITE #: _____
PROTOCOL NUMBER: _____**Headache History Questionnaire****Complete or Circle**

Date of Diagnosis (Episodic migraine):	dd/mmm/yyyy	_____/_____/_____	
Monthly Total of all Headache Days (including migraines):			
Of those, Monthly Total of Migraine Days (only migraines):			
Did you have an accident or injury that may have started your headaches?	YES	NO	
Are your headaches attributed to another disorder?	YES	NO	
Do you have any warnings/symptoms of a headache for a period of time before the headache begins?	YES	NO	
Please describe the severity of your headaches:	Mild	Moderate	Severe

When you have a headache:**Yes No**

Activity/Exercise makes it worse		
Bright lights bother you		
Loud sounds bother you		
Like to stay in a quiet, dark room and try to fall asleep		
Have nausea and/or vomiting		
Feel lightheaded or dizzy		
Certain odors bother you		

My headaches are often brought on by:**Yes No**

Fatigue		
Lying down		
Chewing		
Talking		
Certain Foods		
Stress/Tension		
Stooping		
Certain Medications		
Menstruation		
Alcohol		
Oversleeping		
Washing face		
Coughing		
Shaving		

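### One unconfirmed treatment month above the entry ceiling of 14 headache days defines the separately analysed group, so it catches stable subjects near the ceiling and depends on treatment

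*Combined protocol and SAP*

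**What the plan says.** The inclusion criteria in section 2 set the entry range: "On a monthly basis, at least four, and not more than a total of fourteen (4-14), headache days", with migraine days also between 4 and 14. They add a history condition: "The subject must have a history of at least three consecutive months of stable migraine headaches prior to entering the study". The Treatment Day 1 form checks the 4-14 range again against the 28-day baseline diary.

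The last paragraph under Withdrawal Criteria deals with subjects who later go above the ceiling. They are not withdrawn, but "if she/he exceeds 14 headache days in any of the treatment months, such subjects will be grouped separately during the final study analysis". Two reasons are given. In the earlier trial, "a large percentage of subjects in the first CVS migraine RCT were excluded from randomization because they exceeded 14 headache days". And "If a subject has a “good month” during baseline, but is potentially unstable, she/he might be recruited into the study", against the aim of enrolling stable subjects. The paragraph adds that the earlier trial gave no sign of the device raising headache burden, and that these subjects will be followed to learn more about them.

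Section 4 gives three 28-day treatment months in the first period and three in the second, when all arms receive active treatment. Sections 7 and 8 do not mention the group, say how it will be compared, or say whether three or six months count.

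**The concern.** The paragraph is written about a trait that exists before treatment: a subject admitted on an unusually light month. The rule that is meant to pick out such subjects measures something else, in two respects.

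First, the cut is the entry ceiling itself and one crossing suffices. An eligible subject with an unchanging rate just below 14 gets three to six chances to cross it by ordinary fluctuation.

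Second, the months that count are treatment months. If the device works, fewer active subjects cross. Membership is then partly a result of allocation, and the flagged and unflagged sets each contain a different selection of subjects from each arm. An efficacy comparison in either set loses the protection of randomisation. With 40 per arm, moving a handful of mainly placebo subjects is enough to matter.

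**Working it through.** **The plan's own figure.** Section 8 gives 40 per arm, SD of the reduction 3.36, difference 2.13, alpha 0.05, power 80%. Two-sided, n = 2 × (1.960 + 0.842)² × 3.36² / 2.13² = 39.1, rounded up to 40; noncentral-t power at 40 per arm is 80.0%. The figure reproduces. The plan gives no figure for how many subjects will exceed 14 days.

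**Size of the monthly noise.** The documents give no within-subject month-to-month SD. If all the variance of the change were monthly noise, the SD would be 3.36/√2 = 2.38. A binomial count over 28 days with mean 8 has SD √(28 × 8/28 × 20/28) = 2.39. The binomial model is therefore in line with the plan's SD. If part of the 3.36 is variation in response, the true noise is smaller.

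**Chance that a stable subject is flagged.** For true mean m, q = P(X > 14) with X ~ Binomial(28, m/28). Over k independent months with no treatment effect, P(flag) = 1 − (1 − q)^k.

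| True mean | q | 3 months | 6 months |
|---|---|---|---|
| 7.8 | 0.004 | 1.1% | 2.1% |
| 10 | 0.040 | 11.6% | 21.9% |
| 12 | 0.170 | 42.8% | 67.2% |
| 14 | 0.425 | 81.0% | 96.4% |

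At 12, for example, 1 − 0.830³ = 0.428. A normal model with SD 2.38 and cut 14.5 gives 37.8% and 61.3% at 12. The 7.8 row is the mean baseline implied by the first trial's active arm (3.6/0.461). That is in migraine days; headache days will be at least as high.

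**Dependence on treatment, one subject.** Take a true baseline of 12 and, as an assumption, apply the first trial's migraine-day changes to headache days.
- Placebo, −0.9: mean 11.1, q = 0.0956, three-month probability 26%.
- Active, −3.6: mean 8.4, q = 0.0078, three-month probability 2%.

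**Dependence on treatment, cohorts.** Simulated cohorts used gamma-distributed true means with (mean, SD) of (8, 3), (9, 3) and (10, 4). Baseline was kept at 4-14, and noise was binomial or mildly overdispersed (intra-subject correlation 0.03). With assumed falls of 10% on placebo and 40% on active, the number flagged in the first period is about 2.0 to 7.5 of 40 on placebo and 0.1 to 1.2 of 40 on active.

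**Share of the flagged group that is stable.** Taking stable as a true mean of 14 or less, the three cohorts above give 73% to 90% over three months with no effect. They assume, however, that only about 1.5% to 6% of enrolled subjects are truly above 14. Wider assumptions move the answer a long way (three months):
- gamma means 8-13, SD 2.5-5, binomial noise: 63% to 90% with no effect, 54% to 85% with a 0.9-day fall, 24% to 57% with a 3.6-day fall;
- the same with a 0.9-day fall, if the three history months also had to lie in 4-14: 89% to 97%;
- a distinct unstable class forming 1% to 34% of those enrolled, 0.9-day fall: 10% to 92%. The share drops below half once that class reaches about 5% of enrolled subjects (stable mean 8) or 12-13% (stable mean 10).

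**Alternative flags, no effect, first three cohorts.**
- More than 42 headache days in the 84: false flags among stable subjects fall from 8%-23% to 1%-5%. Detection of subjects truly above 14 falls from about 90%-92% to 66%-71%.
- Baseline diary of 12-14 days: 82% to 93% of the group is at or below 14 (current rule 73% to 90%), and detection is 63% to 79%.

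**The case against.** The strongest defence is that the paragraph never calls the group unstable. It speaks only of potential instability, and the sub-population it wants data on is, in so many words, those who go above 14 in a treatment month. The rule finds exactly those people. A subject who swings across 14 around a mean of 11 or 12 may be just the kind of instability meant. No endpoint in section 7 uses the group, section 8 specifies intent-to-treat for the primary aim, and typical subjects are seldom flagged.

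Much of this stands. It limits the point to an additional grouping whose use is left undefined. It also rules out two stronger readings. A reader might infer that the group would consist mostly of stable subjects. The documents do not support that: they give neither the share of unstable enrollees nor the spread of headache days, and the range above runs from 10% to 97%. A reader might also infer that flagged subjects are dropped from the primary comparison. The plan does not say so, and its intent-to-treat statement points the other way.

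The defence does not answer the second half of the concern. Even if the group is exactly what the sponsor wants to observe, its membership is affected by treatment, and the plan sends it to the final analysis without saying that arms will not be compared within or outside it.

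**Conclusion.** The point holds in a limited form. The rule cannot tell an unstable subject from a stable one near the ceiling: at true means of 12 to 14, the chance of being flagged by noise alone is 43% to 81% in three months and 67% to 96% in six. Near 8 days it is about 1% to 3%. How much of the flagged group would be misclassified cannot be settled from the documents.

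The firmer conclusion is that the flag is a post-randomisation outcome. If the device lowers headache days, the flag will fall mainly on placebo subjects, and any arm comparison conditional on it is biased by selection. That conclusion does not depend on the unknown share of unstable subjects. The counts (about 2 to 7.5 of 40 against 0 to 1 of 40) rest on the assumed distributions, independent months, and falls of 10% and 40%.

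**What to change.** In the last paragraph under Withdrawal Criteria and in section 8, replace the separate grouping with an outcome: the proportion of subjects with any treatment month above 14 headache days, reported by randomised arm in all randomised subjects. Use the first treatment period for the comparison with placebo, because all arms are on active treatment after that. State how a month with missing diary days is counted. This answers the headache-burden question directly, with randomisation intact. Add that no between-arm efficacy comparison will be made within the flagged subjects or after excluding them, and that any listing of them is descriptive.

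A subgroup with 12-14 baseline headache days should not be used as a substitute. It did worse than the present rule in every scenario tested, and it relies on the very month the paragraph distrusts. An averaged flag (more than 42 of 84 days) can be an optional descriptive sensitivity, with its loss of detection stated; it too is measured after randomisation.

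The cost is a few sentences of wording. The diary already holds the data. What is given up is a separate efficacy analysis of this group, which could not have been interpreted by arm.
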